6.11.2. Analyses of Multiplicity Adjusted Objectives

A graphical approach for multiple comparisons will be used to strongly control the overall Type I error (2-sided alpha level of 0.05) for testing the treatment effect for the primary objective (H1) and the following multiplicity adjusted objectives: superiority of LY900014 compared with Humalog for (H2) 1-hour postprandial glucose (PPG) during MMTT at Week 16, (H3) 2-hour PPG during MMTT at Week 16, (H4) change from baseline to Week 16 in HbA1c, (H5) duration (in minutes and percentage of time) with glucose values between 70 and 180 mg/dL (3.9 and 10.0 mmol/L), both inclusive, normalized to a 24-hour period at Week 16, and (H6) duration (in minutes and percentage of time) with glucose values between 70 and 180 mg/dL (3.9 and 10.0 mmol/L), both inclusive, normalized to daytime (0600 hours to midnight) at Week 16. Analyses will be performed for both the efficacy estimand and ITT estimand.

The graphical testing scheme is displayed in [Figure ITRO 6.1](#). The study total alpha level (or study-wise type I error) is preset to be 5% for each estimand. All the hypotheses are connected by lines with arrowheads indicating the directions of testing paths. The initial allocation of study total alpha for each hypothesis is located within the same node of the hypothesis. The study total alpha level will be used for the primary objective in the initial step. The alpha level will be allocated to other key endpoints based on the weights in testing paths once the primary endpoint is successfully demonstrated. If 1 of the remaining hypotheses is successfully demonstrated with the preserved alpha level, its preserved alpha will be allocated to the remainder of the hypotheses by the weights in the paths. The iterative test procedure continues until none of the remaining hypotheses can be demonstrated with their preserved alphas or all hypotheses are demonstrated successful.

An ANCOVA model with strata (country, HbA1c stratum ($\leq 7.5\%$, $> 7.5\%$), and patient's personal CGM or FGM use during the study) and treatment as fixed effects and baseline as a covariate will be used to analyze the 1-hour and 2-hour PPG for both the efficacy (data collected prior to discontinuation of IP) and ITT (all data collected regardless of IP use) estimands. However, if the percentage of the patients with missing MMTT data at baseline is higher than 15%, a constrained longitudinal data analysis model (Liu et al. 2009; Lu 2010) will be used instead.

Duration with glucose values between 70 and 180 mg/dL (3.9 and 10.0 mmol/L), both inclusive, normalized to 24-hour period and to daytime will be analyzed using a similar MMRM model as used for the primary endpoint.

The superiority testing on change from baseline to the study primary endpoint in HbA1c will be assessed by the same analysis used for the primary objective. The analyses for the ITT and efficacy estimands are described in Section 6.11.1. If the p-value is less than the alpha level allocated by the graphical approach, the superiority of LY900014 to insulin lispro will be achieved.

[figure not shown]

Figure ITRO 6.1. Testing scheme for primary and multiplicity adjusted objectives.

6.11.3. Sensitivity Analyses for Missing Data

A missing-not-at-random-based analysis will be performed for both the efficacy and ITT estimands to assess sensitivity to departures from the missing-at-random (MAR) assumption. The tipping-point approach that will be used is similar to a progressive stress test (Ratitch et al. 2013). The basic idea is to impute the missing values and add a value (delta) to the imputed values of the experimental treatment group and perform an analysis for the primary endpoint on the delta-adjusted data set to see whether the conclusion of the primary analysis is overturned. If not, a larger delta is chosen and the process repeated until the primary result is overturned. If the delta required to overturn the primary result is not a plausible departure from MAR, then the primary result is robust to plausible departures from MAR. The initial delta is set to 0.1 with an

increment of 0.1. Imputation under the noninferiority null method (where delta equals the NIM) will be included as a special case of the progressive stress test.

For the ITT estimand, the reference group will be as described for the FDA primary analysis, and ANCOVA on the change from baseline to Week 16 in HbA1c will be used.

For the efficacy estimand, the reference group will be the Humalog treatment group. Imputation will be for all longitudinal visits.

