10.3.3.1.1. Sensitivity Analyses for Missing Data

A missing-not-at-random-based analysis will be performed for both the efficacy and ITT estimands to assess sensitivity to departures from the missing-at-random (MAR) assumption. The tipping-point approach that will be used is similar to a progressive stress test (Ratitch et al. 2013). The basic idea is to impute the missing values and add a value (delta) to the imputed values of the experimental treatment group and perform an analysis for the primary endpoint on the delta-adjusted data set to see whether the conclusion of the primary analysis is overturned. If not, a larger delta is chosen, and the process repeated until the primary result is overturned. If the delta required to overturn the primary result is not a plausible departure from MAR, then the primary result is robust to plausible departures from MAR. The initial delta is set to 0.1 with an increment of 0.1. Imputation under the noninferiority null method (where delta equals the NIM) will be included as a special case of the progressive stress test.

For the ITT estimand, the reference group will be as described for the FDA primary analysis, and ANCOVA on the change from baseline to Week 16 in HbA1c will be used.

For the efficacy estimand, the reference group will be the Humalog treatment group. Imputation will be for all longitudinal visits.

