5.2. Determination of Sample Size

Approximately 420 patients will be randomized in order that approximately 368 patients complete the study through the primary endpoint at Week 16.

[figure not shown]
The primary objective of this study is to test the hypothesis that LY900014 is noninferior to Humalog on glycemic control as measured by change from baseline to Week 16 in HbA1c in patients with T1D when administered in a double-blind manner using CSII with bolus doses delivered 0 to 2 minutes prior to the meal.

Patients will be randomized in a 1:1 ratio to double-blind LY900014 with bolus dose delivered 0 to 2 minutes before meals or double-blind Humalog with bolus doses delivered 0 to 2 minutes before meals. Assuming a noninferiority margin (NIM) of 0.4%, no true difference between treatment groups, and a standard deviation (SD) of 0.88%, 368 completers (184 in each treatment group) will provide at least 99% power to show noninferiority between LY900014 and Humalog in change from baseline to Week 16 in HbA1c using the upper limit of a two-sided 95% confidence interval (CI) (LY900014 – Humalog). Assuming a 12% dropout rate for 16 weeks, approximately 420 patients will need to be randomized. This sample size also has 90% power to show noninferiority between LY900014 and Humalog using a 0.3% NIM at Week 16.

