For non-FDA submissions, the primary efficacy comparison will be based on the contrast between LY900014 and Humalog at Week 16 (Visit 13) from the MMRM analysis of change from baseline in HbA1c including data collected from all randomized patients prior to permanent discontinuation of IP through Week 16 (efficacy estimand). The model for the analysis of the primary efficacy endpoint of change from baseline in HbA1c will include the fixed class effects of treatment, strata (country and patient's personal CGM or FGM use during the study), visit, and treatment-by-visit interaction, as well as the continuous, fixed covariates of baseline value. An unstructured covariance structure will be used to model the within-patient errors. Significance tests will be based on LS means and Type III tests. If this analysis fails to converge, the following covariance structures will be tested in order:

- Toeplitz with heterogeneity

- autoregressive with heterogeneity
- compound symmetry with heterogeneous variances
- Toeplitz
- autoregressive
- compound symmetry without heterogeneous variances

The first covariance structure that converges will be used. The Kenward-Roger approximation will be used to estimate denominator degrees of freedom.

For both primary analysis approaches, LY900014 will be declared noninferior to Humalog if the upper limit of the 2-sided 95% CI for the LS mean difference in the change from baseline in HbA1c for LY900014 minus Humalog is below +0.4%. In addition, the 95% CI for the treatment difference will be compared to an alternative NIM of +0.3%. Both estimands will be tested at the full significance level of 0.05.

In addition to the primary objective, the superiority of LY900014 in controlling HbA1c compared with Humalog will also be assessed for each analysis approach described above. If the p-value is less than the alpha level from the graphical approach allocated to the superiority hypothesis, LY900014 will be declared superior to Humalog.

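### For the efficacy estimand, the tipping-point delta is measured from the Humalog arm but read as a departure from MAR, which modestly overstates robustness near the margin when LY900014 looks worse

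*SAP*

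**What the plan says.** SAP 6.11.3 plans a tipping-point analysis for each estimand. Missing values are imputed and delta is added to the imputed LY900014 values only. Delta starts at 0.1 and rises in steps of 0.1 until the primary conclusion is overturned. The section's criterion is: "If the delta required to overturn the primary result is not a plausible departure from MAR, then the primary result is robust". For the efficacy estimand it specifies: "For the efficacy estimand, the reference group will be the Humalog treatment group. Imputation will be for all longitudinal visits". Protocol 10.3.3.1.1 says the same: "For the efficacy estimand, the reference group will be the Humalog treatment group". Both sections include the noninferiority null, with delta equal to the margin, as a special case.

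Three other places bear on this:

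- **Primary analysis, efficacy estimand.** This is an MMRM (SAP 6.11.1), which SAP 6.3 justifies under MAR. Noninferiority is declared if the upper 95% confidence limit for the change in "HbA1c for LY900014 minus Humalog is below +0.4" percentage points.
- **Meaning of reference.** SAP 6.11.3 does not define the term. SAP 6.11.1 uses it for the data from which missing values are imputed, and for the ITT estimand those data come from the patient's own treatment group.
- **Population.** SAP Table ITRO 6.2 limits the efficacy-estimand HbA1c analysis to patients with a baseline and at least one post-baseline value on IP, taken from Visits 8, 10 and 13.

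**The concern.** A tipping-point analysis should start from the primary assumption and move away from it. Under MAR, a missing LY900014 value follows the LY900014 on-treatment course. If it is drawn from a Humalog model instead, delta = 0 does not return to that assumption, because the imputed LY900014 values have already moved toward no difference between arms.

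In a superiority test that shift is a stress. In a noninferiority test with LY900014 observed to be worse, it helps the sponsor. The first step or two of the grid may then only undo the favourable start, yet be reported as departures from MAR that the result survived. This is the only check on MAR that SAP 6.11.3 specifies for the non-FDA primary analysis. A tipping analysis also matters most when the estimate is close to the margin, and that is where the offset counts.

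**Working it through.** **Inputs from the documents.** SD 0.88, 184 completers per arm, "no true difference between treatment groups" and 12% dropout (SAP 5.2); margin 0.4 and alternative margin 0.3 (SAP 6.11.1). The documents give no tipping delta.

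**Assumptions.** The dropout rate stands in for the missing fraction m in the LY900014 arm (6% and 20% are also shown). The values of k and the visit correlations are assumed.

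**The plan's own figures.** The standard error is 0.88 × √(2/184) = 0.0917.

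- Margin 0.4: 0.4/0.0917 − 1.96 = 2.40, power 99.2%.
- Margin 0.3: 0.3/0.0917 − 1.96 = 1.31, power 90.5%.
- Randomized: 368/0.88 = 418.2, so 419.

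These agree with the stated values of at least 99%, 90% and approximately 420.

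**Tipping formula.** The half-width is h = 1.96 × 0.0917 = 0.180. With the Humalog reference, the mean difference among LY900014 dropouts is (1 − k)D + delta. The overall difference is then

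(1 − m)D + m[(1 − k)D + delta] = D − mkD + m·delta.

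Setting this plus h equal to 0.4 gives

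- own-arm MAR: delta = (0.4 − h − D)/m
- Humalog reference: delta = (0.4 − h − D)/m + kD

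The offset is kD. For example, at D = 0.20 and m = 0.12, 0.0202/0.12 = 0.17 under MAR. Adding kD gives 0.37 at k = 1 and 0.27 at k = 0.5.

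| D | Own-arm MAR | Humalog, k = 1 | Humalog, k = 0.5 |
|---|---|---|---|
| −0.20 | 3.50 | 3.30 | 3.40 |
| 0 | 1.83 | 1.83 | 1.83 |
| 0.10 | 1.00 | 1.10 | 1.05 |
| 0.15 | 0.58 | 0.73 | 0.66 |
| 0.20 | 0.17 | 0.37 | 0.27 |

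At D = 0.20 and k = 1, the pair (Humalog reference against MAR) is 0.54 against 0.34 for m = 6%, and 0.30 against 0.10 for m = 20%.

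**Ceiling.** Noninferiority at 0.4 requires D < 0.4 − 0.18 = 0.22, so the overstatement cannot exceed about 0.22. At the 0.3 margin it requires D < 0.12, with a ceiling of about 0.12.

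**How large k is.** A simulation used 210 per arm, 12% missing, three visits, regression-based multiple imputation with Rubin's rules, delta added at Week 16, visit correlation 0.5 or 0.7, and 300 replicates per setting. At D = 0.20 the overstatement was:

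- no earlier post-baseline visit: 0.19 to 0.20
- one earlier visit: 0.12 to 0.13
- two earlier visits: 0.08 to 0.10

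At D = −0.15 the sign reversed (−0.05 to −0.17).

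**On the 0.1 grid at D = 0.20.** Own-arm MAR (0.17) survives 0.1 and is overturned at 0.2. With one or two earlier visits (about 0.25 to 0.30) the result survives 0.2. At k = 1 (0.37) it survives 0.3.

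**Where a reading changes.** Take delta = 0.4 as the benchmark. Under MAR, noninferiority survives if D < 0.220 − 0.12 × 0.4 = 0.172. With the Humalog reference the limit is 0.172/(1 − 0.12k), which is 0.183 at k = 0.5 and 0.196 at k = 1. If the true difference is 0 and the standard error 0.0917, the estimate falls in that window with probability about 0.7% (k = 0.5) or 1.4% (k = 1).

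**The case against.** The strongest reply has four parts.

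1. **Size.** The k = 1 figures describe dropouts with no post-baseline HbA1c, and Table ITRO 6.2 excludes such patients from the efficacy-estimand analysis. This stands. A reader might infer from 0.37 against 0.17 that robustness is overstated about twofold, or that delta is too large by the whole of D. The documents support neither as the expected size; k = 1 is an upper bound.
2. **Direction.** If LY900014 looks better, which is the direction of the planned superiority test, the Humalog reference is conservative. This also stands.
3. **Rationale.** The noninferiority null places LY900014 at Humalog plus the margin, so a Humalog anchor is coherent for that special case. This stands for the special case. It does not justify reading every other delta as a departure from MAR.
4. **Underspecification.** SAP 6.11.3 neither defines the reference group nor says whether delta is added at every imputed visit or only at Week 16. If own-arm imputation was intended, the problem is one of wording. Adding delta at each visit in a sequential imputation would also change the effective delta. Both points are fair, and both call for clarification. The usage in SAP 6.11.1 still makes imputation from Humalog the natural reading.

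**Conclusion.** The point holds with a limited size. On the natural reading, the efficacy-estimand delta is an offset from Humalog, and the departure from MAR is delta − kD. The error favours noninferiority only when D > 0. At D = 0.20 the likely overstatement is about 0.08 to 0.13 HbA1c percentage points, roughly one grid step, with 0.20 as the upper bound. This rests on 12% missing, visit correlations of 0.5 to 0.7, and imputation that conditions on earlier visits.

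A reader might go further and conclude that the primary noninferiority test is biased, or that a result on the margin would automatically be declared robust. The documents do not support either. The MMRM and its decision rule do not use this imputation. SAP 6.11.3 leaves plausibility to judgement, and a small tipping delta would look fragile under either reference. The robustness reading changes only when the estimate lies near the margin. The correction is still worth making before unblinding, because the reported quantity is not what the section says it is. The efficacy and ITT deltas are also measured from different kinds of reference.

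**What to change.** In SAP 6.11.3, for the efficacy estimand, impute missing values within each patient's own arm under MAR, then add delta to the imputed LY900014 values in 0.1 steps. State whether delta is applied at every imputed visit or only at Week 16. Keep the Humalog reference only for the noninferiority-null case (Humalog plus the margin), labelled as a separate analysis. Align Protocol 10.3.3.1.1, or record the change and its reason in the SAP.

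If the Humalog reference is kept throughout, describe delta as an offset from Humalog and report the implied departure from MAR beside each value. If own-arm imputation was always intended, say so.

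The cost is a sentence or two in the SAP and one changed imputation step. No new data are needed, and the primary analysis and sample size do not change.

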6.11.4. Other Secondary Efficacy Analyses

The analyses described below will include data collected from all randomized patients prior to permanent discontinuation of IP. The longitudinal observations of actual and change from baseline in HbA1c up to Week 16 will be analyzed using the same MMRM model as for the analysis of the primary outcome. For the following secondary efficacy endpoints, an MMRM model with fixed class effects of treatment, strata (pooled country, HbA1c stratum ($\leq 7.5\%$, $>7.5\%$) and patient's personal CGM or FGM use during the study), visit, and treatment-by-visit interaction, as well as the continuous, fixed covariates of baseline value.

- actual and change from baseline 1,5-Anhydroglucitol (AG) values
- actual and change from baseline 10-point self-monitored blood glucose (SMBG) values (fasting, 1 hour post morning meal, 2 hours post morning meal, pre midday meal, 1 hour post midday meal, 2 hours post midday meal, pre evening meal, 1 hour post evening meal, 2 hours post evening meal, and bedtime)
- actual and change from baseline in total, basal, and bolus insulin doses and bolus/total insulin dose ratios
- actual and change from baseline in CGM derived time in hypoglycemia and time in hyperglycemia, defined in Section 6.13.

Three 10-point SMBG profiles are expected to be collected during the 2 weeks prior to Visits 4, 8, and 13. Valid SMBG profiles will be used for analysis, defined as having non-missing values at ≥ 6 time points per day among the 10 pre-specified time points and being collected during 2 weeks prior to a given visit. For each time point, the average of the corresponding SMBG values from the valid SMBG profiles will be used for analysis. The SMBG and the excursion for each meal category (that is, morning meal, midday meal, and evening meal) calculated using the average values at the corresponding time points will be used for analysis.

The basal, bolus, total doses and bolus/total insulin dose ratios for each visit will be calculated as the mean of the doses for the last 3 days prior to the visit. Doses will be summarized in U and U/kg.

Derivation and analysis of CGM endpoints are described in Section 6.13.

The following endpoints, collected from the MMTT, will be analyzed using the ANCOVA model with strata (pooled country, HbA1c stratum ($\leq 7.5\%$, $> 7.5\%$), and patient's personal CGM or FGM use during the study) and treatment as fixed effects and baseline as a covariate:

- actual and change from baseline in fasting glucose (average of measurements at time -15 and 0), and PPG at 15, 30, 60, 120, 180, and 240 minutes after the meal
- PPG excursions at time 15, 30, 180, and 240 minutes after the meal (PPG minus fasting glucose)

Sensitivity analysis for PPG and excursions may be performed to exclude patients whose PPG and excursion could be affected by factors including MMTT consumption amount (for example, partial MMTT was consumed).

Treatment comparisons for the proportion of patients with HbA1c $< 7.0\%$ and $\leq 6.5\%$ will be analyzed using a longitudinal logistic regression with repeated measurements conducted by a generalized linear mixed model including independent variables of treatment, baseline HbA1c value, visit, baseline HbA1c-by-visit interaction, and treatment-by-visit interaction. An unstructured covariance structure will be used.

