7.2. Method of Treatment Assignment

Patients who meet all criteria for enrollment will be randomized to double-blind treatment at Visit 4. Assignment to treatment groups will be determined by a computer-generated random sequence using an interactive web-response system (IWRS). The IWRS will be used to assign all vials containing double-blind IP during the study and open-label Humalog during the lead-in

period. Site personnel will confirm that they have located the correct vials by entering a confirmation number found on the vials into the IWRS.

Patients will be randomized to 1 of 2 treatment groups in 1:1 ratio. Stratification will be by country, HbA1c stratum ($\leq 7.5\%$, $> 7.5\%$ at Visit 1), and patient's personal CGM or FGM use during the study (yes/no).

Patients will begin using double-blind IP in their pumps immediately following successful completion of the Visit 4 MMTT. Patients will fill a new pump reservoir and infusion set with IP, then insert a new pump infusion set cannula and begin infusion of IP prior to leaving the investigative site.

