For continuous longitudinal secondary endpoints, the MMRM model similar to that for the primary analysis will be used with HbA1c stratum ($\leq 7.5\%$, $> 7.5\%$) added as a fixed effect. Duration and percent time in range, time in hypoglycemia and time in hyperglycemia derived from CGM data will also be analyzed using MMRM model with HbA1c stratum ($\leq 7.5\%$, $> 7.5\%$) as a fixed effect. Continuous nonlongitudinal secondary endpoints will be analyzed using the ANCOVA model with treatment and strata as fixed effects and baseline as a covariate.

Treatment comparisons for the proportion of patients with HbA1c $< 7.0\%$ and $\leq 6.5\%$ will be analyzed using a longitudinal logistic regression with repeated measurements conducted by a generalized linear mixed model including independent variables of treatment, baseline HbA1c value, visit, baseline HbA1c by visit interaction, and treatment-by-visit interaction. Actual and change from baseline in basal, bolus, and total dose, as well as the bolus/total insulin dose ratio will be analyzed by the MMRM models described in Section 10.3.1.

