6.2. Adjustments for Covariates

Stratification factors of this study include country, HbA1c stratum ($\leq 7.5\%$, $> 7.5\%$), and patient's personal CGM or FGM use during the study. Stratification factors will be entered into the IWRS for randomization and also collected in the database by electronic case report form (eCRF) or central laboratory. The analysis models will use the stratification factors as collected at randomization in the database as fixed effects.

For the primary analysis of HbA1c, the stratification factor of HbA1c stratum will not be included. Instead, the continuous value of baseline (Visit 4) HbA1c will be included in the analysis models.

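### The logistic model for the HbA1c-target proportions omits personal CGM/FGM use and country, contrary to SAP 6.2 and with no reason given; the cost is small.

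*SAP*

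**What the plan says.** Protocol 7.2 and SAP 5.3 stratify randomization by country, HbA1c stratum (≤7.5%, >7.5% at Visit 1) and personal CGM or FGM use (yes/no). SAP 6.2 then sets a general rule: "The analysis models will use the stratification factors as collected at randomization in the database as fixed effects". The one exception it states is for the primary HbA1c analysis, where the HbA1c stratum is dropped: "Instead, the continuous value of baseline (Visit 4) HbA1c will be included in the analysis models".

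The HbA1c ANCOVA and MMRM in SAP 6.11.1 keep country and CGM/FGM use. So do the MMRM and mixed-meal ANCOVA models in SAP 6.11.4.

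The HbA1c-target model in SAP 6.11.4 is a "generalized linear mixed model including independent variables of treatment, baseline HbA1c value, visit, baseline HbA1c-by-visit interaction, and treatment-by-visit interaction". Protocol 10.3.3.2 gives the same list: "treatment, baseline HbA1c value, visit, baseline HbA1c by visit interaction, and treatment-by-visit interaction". The SAP adds, "An unstructured covariance structure will be used", with no fallback if that fails. Neither document gives a reason for leaving out the two factors.

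Objective 13 is an other secondary objective, and SAP 6.5 makes no multiplicity adjustment for it.

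**The concern.** Patients are randomized within country and CGM/FGM use, so the natural analysis conditions on both, and SAP 6.2 says as much. The sponsor expects CGM/FGM use to matter: Protocol 7.1.2.1 gives possible differences between users and non-users as the reason for stratifying, and SAP 6.14.1 makes it a subgroup for HbA1c.

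The responder analysis is therefore adjusted differently from the continuous HbA1c analysis it supports. A programmer who reads SAP 6.2 and SAP 6.11.4 together could also defend two different models for a named secondary endpoint. At stake are some power, the meaning of the reported odds ratio, and consistency. The primary conclusion is not affected.

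**Working it through.** **1. The plan's own figures.** The documents give power only for HbA1c noninferiority (SAP 5.2: 184 completers per arm, SD 0.88%).
- SE = 0.88 × √(2/184) = 0.0917.
- Margin 0.4%: 0.4/0.0917 − 1.96 = 2.40, so power is 99.2% (stated: at least 99%).
- Margin 0.3%: 0.3/0.0917 − 1.96 = 1.31, so power is 90.5% (stated: 90%).
- Randomized: 368/0.88 = 418.2, so 419 (stated: about 420).

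These reproduce. No power is stated for the target proportions, so n = 368 is carried forward and everything else below is an assumption.

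**2. Approximate size.** Assume 30% responders and stratum log-odds with SD 0.3 to 0.5.
- Attenuation of the log odds ratio when strata are ignored, 1/√(1 + 0.346 × SD²): 0.985 at SD 0.3 and 0.959 at SD 0.5, a pull toward 0 of about 1.5% to 4%.
- Relative efficiency of the test that ignores strata, 1 − p(1−p) × SD²: 1 − 0.21 × 0.09 = 0.981, and 1 − 0.21 × 0.25 = 0.948. If power is 65% with the factors (1.96 + 0.385 = 2.345), multiplying 2.345 by √0.981 or √0.948 gives about 64.2% or 62.7%, a loss of about 1 to 2.5 points.

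Both formulas describe a single-visit model without other covariates.

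**3. Simulation.** Patients were randomized 1:1 in permuted blocks within country × HbA1c stratum × CGM use, n = 368. A Week 16 logistic regression stood in for the repeated-measures model and was fitted with and without pooled country and CGM use; baseline HbA1c was in both. Assumptions: true log odds ratio 0 or 0.8; 5, 8 or 12 countries; country SD 0 to 0.8 and CGM effect 0 to 0.6 on the logit scale; target rate 20% or 7%; 1,500 to 2,000 runs each. Selected results at a true log odds ratio of 0.8 (without → with the factors):

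| Countries | Country SD / CGM effect | Rate | Estimate | SE | Power, % | Runs with a diverging term, % |
|---|---|---|---|---|---|---|
| 5 | 0.4 / 0.3 | 20% | 0.802 → 0.844 | 0.341 → 0.351 | 67.5 → 69.2 | 1.5 |
| 8 | 0.8 / 0.6 | 20% | 0.731 → 0.831 | 0.332 → 0.361 | 60.3 → 64.5 | 16.0 |
| 12 | 0 / 0 | 20% | 0.814 → 0.865 | 0.344 → 0.359 | 66.0 → 67.7 | 23.6 |
| 12 | 0.8 / 0.6 | 20% | 0.750 → 0.868 | 0.332 → 0.366 | 63.2 → 67.0 | 37.2 |
| 8 | 0.8 / 0.6 | 7% | 0.763 → 0.874 | 0.493 → 0.542 | 33.4 → 36.3 | 73.7 |

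Across all scenarios:
- Adding the factors raises the SE by about 3% to 13% and moves the estimate away from 0 by more, so power rises by about 1 to 4 points.
- Part of that gain is not real. With no country or CGM effect at all (third row), power still rises by 1.7 points, and the adjusted estimates of 0.82 to 0.90 overshoot the true 0.8. That is small-sample bias.
- Type I error is 3.7% to 5.7% without the factors and 4.4% to 6.1% with them.
- A country or CGM coefficient diverges in about 2% to 37% of runs at the 20% rate and 29% to 97% at the 7% rate, typically where a country has no responders.

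**4. Second check.** A separate single-visit simulation with 8 countries and its own assumed effects gave an SE rise of about 3% to 6% and a power change of about 0 to 4 points, with almost none from CGM/FGM use alone. Separation occurred in about 5% to 9% of runs at its lower target rate. The separation figures from the two exercises differ widely, so they establish the risk but not its size.

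**The case against.** The strongest defence is that the short model is deliberate. Protocol and SAP list identical terms, and a specific list normally overrides a general sentence. Protocol 10.3.1 attaches strata to the MMRM and ANCOVA models. The binary and count models elsewhere also omit them: hypoglycemia (SAP 6.12.3.1), the HbA1c composite (SAP 6.11.5), and CGM event rates and target attainment (SAP 6.13). Baseline HbA1c, likely the strongest predictor, is in the model and covers the third stratification factor. Pooled countries may hold as few as 10 patients (SAP 6.4), about 5 per arm. Entry requires HbA1c of at least 6.5%, so ≤6.5% may be uncommon, and this model has no convergence fallback.

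Much of this stands. A reader might infer that omitting the factors loses precision at no benefit. That does not hold. Losing precision is the linear-model argument; in logistic regression the SE falls when the factors are left out, and because the odds ratio is non-collapsible the two models estimate different quantities. The shorter model also has a real stability advantage. Nor can one infer an invalid test: Type I error stays close to nominal, and the attenuation is toward no difference, so it does not favour LY900014.

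The defence does not explain the departure from SAP 6.2. The documents never cite sparsity as their reason, SAP 6.2 does not exempt binary endpoints, and the sparsity argument scarcely touches a two-level CGM/FGM term.

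**Conclusion.** The point holds as a minor one. The HbA1c-target model departs from SAP 6.2 and from the continuous HbA1c analyses, without explanation. Omission costs about 0 to 4 points of power, mostly attributable to country, and pulls the odds ratio slightly toward 1 relative to the stratum-conditional value. It does not enlarge the SE or materially disturb Type I error.

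The sizes rest on assumed target rates, country numbers and covariate effects that the documents do not give, and on a single-visit stand-in for the planned repeated-measures model. SAP 6.11.4 does not say whether the unstructured covariance applies to patient random effects or to residuals. If it applies to random effects, these would absorb much of the stratum heterogeneity, and the attenuation formula would not apply as written. The endpoint is neither primary nor alpha-controlled.

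**What to change.** In SAP 6.11.4:
- Add personal CGM/FGM use (yes/no) as a fixed effect.
- Add pooled country as in SAP 6.4, collapsed further to region where patient counts are small. Define the regions, which SAP 6.14.1 names but does not compose, and fix the collapsing before data lock.
- Base the collapsing on patient counts, never on whether a country has responders, because that would let the outcome choose the model.
- Prespecify a fallback: if the model does not converge or shows separation, drop country and keep CGM/FGM use.

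The cost is a few lines of text and two terms built from data already collected. The downside is some sparse-cell and convergence risk for the country terms, mainly at ≤6.5%, which the fallback contains. If the sponsor prefers the short model, SAP 6.2 should state the exception and its reason, and the adjusted model should be reported as a sensitivity analysis.
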